### **Study Treatments:**

A0081106 study medication will be provided as pregabalin liquid oral solution or oral capsules. Subjects <4 years of age at Visit 1 or who are enrolling from A0081042 will receive study medication 3 times daily (TID) in equally divided doses. Subjects who are  $\geq 4$  years of age at Visit 1 will receive study medication twice daily (BID) in equally divided doses.

- All eligible pediatric subjects 1 month to 16 years and 11 months of age will take pregabalin in Study A0081106 at a dosage according to their body weight:
  - Pediatric subjects weighing  $\geq 30$  kg will begin pregabalin dosing at 2.5 mg/kg/day (maximum 150 mg/day). Subjects will remain at the starting dose for 8 days until Visit 2. Thereafter, dosing will be flexible based on individual seizure response and tolerability. Pediatric subjects may have their dose adjusted up or down at clinic visits in increments of no more than 2.5 mg/kg/day (maximum 150 mg/day) to daily dose levels of 5.0 (maximum 300 mg/day), 7.5 (maximum 450 mg/day), or 10.0 mg/kg/day (maximum 600 mg/day).
  - Pediatric subjects with body weight <30 kg will begin pregabalin dosing at 3.5 mg/kg/day until Visit 2. Thereafter, dosing will be flexible based on individual seizure response and tolerability. Pediatric subjects may have their dose adjusted up or down at clinic visits in increments of no more than 3.5 mg/kg/day to daily dose levels of 7.0, 10.5, or 14.0 mg/kg/day. This 40% higher dose per kg in pediatric subjects with body weight <30 kg is needed to achieve exposures similar to those of adults or pediatric subjects weighing  $\geq 30$  kg.
- All eligible adult subjects 17 to 65 years of age will begin dosing of pregabalin in Study A0081106 at the level of 150 mg/day. Subjects will remain at this dose for 8 days until Visit 2. Thereafter, dosing will be flexible based on individual seizure response and tolerability. Adult subjects may have their dose adjusted up or down at

clinic visits in increments of no more than 150 mg/day to dose levels of 300, 450, or 600 mg/day.

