## SCHEDULE OF ACTIVITIES

The Schedule of Activities table provides an overview of the protocol visits and procedures. Refer to [STUDY PROCEDURES \(Section 6\)](#) and [ASSESSMENTS \(Section 7\)](#) for detailed information on each procedure and assessment required for compliance with the protocol.

Study Period	Screening/ Baseline		12 Month Treatment Phase												End of Treatment & Taper Phase	
	Clinic Visit Number	Visit 1A	Visit 1B	Visit 2	Visit 3	Visit 4	TC*	Visit 5	TC*	Visit 6	TC*	Visit 7	TC*	Visit 8	Visit 9	
Study Month	Prior Study Subjects	Direct Enroll	Month 1	Month 2	Month 3	Month 4	Month 5	Month 6	Month 7	Month 8	Month 9	Month 10	Month 11	Month 12/EOS/ Early Term g Begin Taper	End Taper/ Follow up	
Study Day	Day 1A a	Day 1B a	8 (±1)	30 (±4)	60 (±4)	90 (±4)	120 (±4)	150 (±4)	180 (±4)	210 (±4)	240 (±4)	270 (±4)	300 (±4)	330 (±4)	365 (±7)	7 days post completion i (±3)
Informed Consent/Assent	X	X														
Record Demographic Information	X	X														
Record Medical History	X b	X														
Record Seizure History	X b	X														
Perform Physical and Neurological Examination	X b	X d							X						X d	
Review Inclusion/Exclusion Criteria	X	X														
Record Antiepileptic Medication History	X b	X														
Record All Prior Medications	X b	X														
Record all concurrent medications and non-drug treatment/procedures (include any ongoing AEDs)	X	X	X	X	X	X	X	X	X	X	X	X	X	X	X	X

Study Period		Screening/ Baseline		12 Month Treatment Phase												End of Treatment & Taper Phase	
Clinic Visit Number		Visit 1A	Visit 1B	Visit 2	Visit 3	Visit 4	TC*	Visit 5	TC*	Visit 6	TC*	Visit 7	TC*	Visit 8	Visit 9		
Study Month		Prior Study Subjects	Direct Enroll	Month 1	Month 2	Month 3	Month 4	Month 5	Month 6	Month 7	Month 8	Month 9	Month 10	Month 11	Month 12/EOS/ Early Term g Begin Taper	End Taper/ Follow up	
Study Day	Day 1A a	Day 1B a		8 (±1)	30 (±4)	60 (±4)	90 (±4)	120 (±4)	150 (±4)	180 (±4)	210 (±4)	240 (±4)	270 (±4)	300 (±4)	330 (±4)	365 (±7)	7 days post completion i (±3)
Perform 12-Lead Electrocardiogram (ECG)	X b	X														X	
Collect and Record Vital Signs	X b	X			X					X			X			X	
Record Height & weight	X b	X								X						X	
Collect Urine Sample for Pregnancy Test c	X b	X								X			X			X	X

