#### **3.1. Treatments and Visits**

[figure not shown]
The day of the last visit (completion of taper phase) of Studies A0081041, A0081042, and A0081105 is designated as Day 1 (Visit 1A) of this study. Baseline values for analysis of change in safety endpoints will be the assessments made prior to initiating double-blind dosing at Visit 1 of Studies A0081041, A0081042, or A0081105. For subjects directly entering Study A0081106 without participation in one of the studies above, baseline values for analysis of change in safety endpoints will be the assessments made at the first visit (Screening Visit 1B) of this study.

For pediatric subjects, pregabalin dosing will initiate at the daily dose of 2.5 mg/kg/day (subjects  $\geq$ 30 kg) or 3.5 mg/kg/day (subjects  $<$ 30 kg) at this visit. Adult subjects who enroll in this study following participation in Study A0081105 will initiate dosing at 150 mg/day. All seizures experienced will be self-recorded by the subject or recorded by their parents/legally acceptable representative as appropriate, in a daily seizure diary beginning at Visit 1 and subsequently throughout the entire study.

Subjects will return for the designated assessments of safety, tolerability, and drug accountability at Week 1 (Visit 2), Month 1 (Visit 3), Month 2 (Visit 4), Month 4 (Visit 5), Month 6 (Visit 6), Month 9 (Visit 7), Month 12/Early Termination (Visit 8), and Follow-up (Visit 9). Investigator site staff will contact the subject and/or parent/caregiver by telephone at least monthly between visits, to address questions, assess safety and adverse events, and ensure compliance with study directives.

At Visit 2 and subsequent visits thereafter, the investigator or designee will review seizure diary data and tolerability with the subject and may adjust the dose at his/her discretion. For pediatric subjects with body weight  $\geq 30$  kg (1 month to 16 years of age), doses may remain the same or be adjusted upward in increments of no more than 2.5 mg/kg/day to daily dose levels of 5.0, 7.5, or 10.0 mg/kg/day. For pediatric subjects with body weight  $< 30$  kg, doses may be adjusted in increments of no more than 3.5 mg/kg/day to daily dose levels of 7.0, 10.5, or 14.0 mg/kg/day. For adult subjects (17 to 65 years of age) doses may be adjusted in increments of 150 mg/day to daily dose levels of 300, 450, or 600 mg/day.

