### **5. STUDY TREATMENTS**

#### **5.1. Allocation to Treatment**

Subjects who complete Visit 1 and meet the eligibility criteria will begin study treatment.

Subjects will be assigned sequentially a subject number at the time of screening (Visits 1A or 1B) by a telerandomization system. An IVRS drug supply management system will assign study medication by assigning appropriate container numbers.

Pediatric subjects with body weight  $\geq 30$  kg will initiate dosing of pregabalin at the daily dose of 2.5 mg/kg/day administered in 2 equally divided doses (BID) in subjects  $\geq 4$  years of age or in 3 equally divided doses (TID) in subjects  $< 4$  years of age for a minimum of 1 week. Thereafter, dosing will be flexible, based on individual seizure response and tolerability. Doses may be adjusted up or down at clinic visits in increments of no more than 2.5 mg/kg/day to daily dose levels of 5.0, 7.5, or 10.0 mg/kg/day. For pediatric subjects with body weight  $< 30$  kg, the daily dose will be adjusted by 40% to an initial daily dose of 3.5 mg/kg/day administered in 2 equally divided doses (BID) in subjects  $\geq 4$  years of age or in 3 equally divided doses (TID) in subjects  $< 4$  years of age for a minimum of 1 week. Thereafter, dosing will be flexible, based on individual seizure response and tolerability. Doses may be adjusted in increments of no more than 3.5 mg/kg/day to daily dose levels of 7.0, 10.5, or 14.0 mg/kg/day. Subjects will maintain a BID or TID dosing regimen throughout study participation based on age at Visit 1 (especially for subjects rolling over

from Study A0081042 who will remain on a TID regimen) to avoid potential dosing error/noncompliance related to regimen switch.

Adult subjects who enroll in this study following participation in Study A0081105 will initiate dosing of pregabalin at the level of 150 mg/day administered daily in 2 equally divided doses (BID) of 75 mg. Thereafter, dosing will be flexible and based on individual seizure response and tolerability. Doses may be adjusted in increments of no more than 150 mg/day to daily dose levels of 300, 450, or 600 mg/day.

The investigator's knowledge of the treatment should not influence the decision to enroll a particular subject or affect the order in which subjects are enrolled.

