- The following assessments are not required to be completed at this visit as the results from Studies A0081041, A0081042, or A0081105 will be used: medical history including seizure related history and antiepileptic medication history; all prior medications; blood samples for hematology and chemistry; urine sample for urinalysis; full physical examination to include height, weight and vital signs and assessment of Tanner Stage for pediatric/adolescent subjects less than 16 years of age; full neurological examination; urine pregnancy test for female subjects who are menarchal, if the results of the urine pregnancy test are positive, the subject will not be eligible for study participation; 12-lead electrocardiogram; CogState battery (completed as part of the last visit of Study A0081041 only); assessment of suicidal ideation and behavior (C-SSRS Since Last Visit version or CBCL) using appropriate test for subject's age.

Note: From Visit 1 onwards, weight of subjects will be recorded in the IVRS at every visit during the course of the study in order to adjust the volume and/or dose of study medication dispensed according to weight change to ensure appropriate study medication administration.

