## **6.2. Clinic Visit 1B (Day 1B): Screening for Subjects Directly Enrolling into Study A0081106 who have not Participated in Studies A0081041, A0081042, or A0081105**

Prior to study entry the following screening procedures will be performed at Visit 1:

- Obtain written informed consent from both parents (if available), or the child's legally acceptable representatives and obtain the child's assent (if applicable).
- Review eligibility per inclusion/exclusion criteria.
- Review and record adverse events.
- Record demographic data (eg, date of birth, sex [at birth], race, etc).
- Record medical history including primary diagnosis.
- Record seizure history including classify seizure type.
- Verify subjects have had an average of at least 3 seizures per month in the 3 months prior to screening. There must not be any seizure free months in the 3 months prior to screening.
- Record complete medical history including seizure related history and antiepileptic medication history.
- Perform complete full physical exam which includes vital signs, including blood pressure (BP) (sitting), pulse and assessment of Tanner Stage for pediatric/adolescent subjects <16 years of age.

- Record height and weight.

Note: From Visit 1 onwards, weight of subjects will be recorded in the IVRS at every visit during the course of the study in order to adjust the volume and/or dose of study medication dispensed according to weight change to ensure appropriate study medication administration.

- Perform full neurological examination.
- Perform electroencephalogram (EEG) (unless the procedure has been performed within 24 months prior to the Screening Visit).
- Perform contrast-enhanced computed tomography (CT) or magnetic resonance imaging (MRI) scan of the brain if it has not been performed within 60 months prior to the Screening Visit or if it is clinically warranted.

Note: in the event that a CT or MRI scan is needed, it should be performed as soon as possible after Visit 1 if it cannot be performed on the day of this visit and must be completed and reviewed prior to Visit 2.

- Record all concomitant medications and non-drug treatments/procedures currently and within 30 days of Visit 1.
- Perform, review and transmit 12-lead ECG to central reader.
- Administer CogState battery (POS subjects 4-16 years of age).

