### 7.2. Vital Signs, Height and Weight

Sitting blood pressure and pulse are to be recorded at the Screening Visit (Visit 1A or 1B), Visits 4, 6, 7 and at the completion of the study. Height (using stadiometer when appropriate) will also be recorded at the Screening Visit (Visit 1A or 1B), Visit 6 and at the

completion of the study. Weight will be recorded at Visits 1A or 1B, 6, and 8. Weight recorded at Visit 1A or 1B and Visit 6 will be used to calculate the dose for subsequent visits.

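### Protocol 6.1/6.2 and 7.2 give incompatible rules for which weight sets a child's dose, so the dosing weight and the date of the change at 30 kg are not fixed

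*Protocol*

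**What the plan says.** Section 7.2 lists the weighing visits, "Weight will be recorded at Visits 1A or 1B, 6, and 8", and then says which weights count for dosing: "Weight recorded at Visit 1A or 1B and Visit 6 will be used to calculate the dose for subsequent visits".

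The note in section 6.1, for subjects coming from the earlier studies, says "weight of subjects will be recorded in the IVRS at every visit during the course of the study in order to adjust" what is dispensed. The same note in 6.2, for direct enrollers, gives the purpose: "in order to adjust the volume and/or dose of study medication dispensed according to weight change".

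The Schedule of Activities marks its "Record Height & weight" row at screening, Visit 6 and Visit 8 only. The procedure lists for Visits 2, 3, 4, 5 and 7 (sections 6.3, 6.4, 6.5, 6.7 and 6.12) contain no weight.

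Dose levels depend on weight band. Below 30 kg the start is 3.5 mg/kg/day, adjusted "in increments of no more than 3.5 mg/kg/day to daily dose levels of 7.0, 10.5, or 14.0 mg/kg/day". At 30 kg or more the start is 2.5 mg/kg/day, adjusted "in increments of no more than 2.5 mg/kg/day to daily dose levels of 5.0, 7.5, or 10.0 mg/kg/day". The Summary, 1.3 and 5.1 allow changes in both directions for the heavier band. Section 3.1 says for that band only that "doses may remain the same or be adjusted upward in increments of no more than 2.5 mg/kg/day". No section says what happens when a child passes 30 kg during the study.

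**The concern.** A weight-based dose is defined only once it is clear which weight is used. Here one rule updates the weight at every visit and the other holds it from Visit 1 to Visit 6 and from Visit 6 to Visit 8. The study enrols from 1 month of age and treats for 12 months, so some children will grow a good deal between those points.

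Two things are at stake for the individual child. A child who stays below 30 kg drifts under the nominal mg/kg level while an old weight is in use. A child who passes 30 kg changes to the lower per-kg levels on a different date depending on which rule is followed. Neither change has anything to do with seizure response or tolerability.

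**Working it through.** **The two rules side by side**

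| Source | Visits with weight | Weights that set the dose |
|---|---|---|
| 6.1 and 6.2 notes | every visit | every visit |
| 7.2 | 1, 6, 8 | 1 and 6 |
| Schedule and visit lists | 1, 6, 8 | not stated |

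The notes cannot be limited to dispensed volume, because they name dose as well.

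**Age of the dosing weight.** Planned clinic days (Schedule of Activities) are 1, 8, 30, 60, 120, 180, 270 and 365.
- 7.2: 180 − 1 = 179 days, then 365 − 180 = 185 days.
- 6.1/6.2: the gaps are 7, 22, 30, 60, 60, 90 and 95 days, so at most 95. With the windows at Visit 7 (±4) and Visit 8 (±7): 372 − 266 = 106 days.

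**Drift when the weight is not updated.** Actual dose = nominal dose / (1 + g), where g is the proportional weight gain since Visit 1. The documents give no growth figures, so g is an assumed range. At a nominal 14.0 mg/kg/day:
- g = 10%: 14.0 / 1.10 = 12.7
- g = 50%: 14.0 / 1.50 = 9.3
- g = 100%: 14.0 / 2.00 = 7.0, which is two listed levels lower.

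**Matching levels at 30 kg.** The protocol says the dose per kg is 40% higher below 30 kg. The listed levels reproduce this: 3.5/2.5 = 7.0/5.0 = 10.5/7.5 = 14.0/10.0 = 1.40. The matching moves are therefore 3.5 to 2.5, 7.0 to 5.0, 10.5 to 7.5 and 14.0 to 10.0.

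**When 14.0 can be reached.** Every child below 30 kg starts at 3.5. With one step of 3.5 at each scheduled visit, the level is 7.0 at Visit 2 (Day 8), 10.5 at Visit 3 (Day 30) and 14.0 at Visit 4 (Day 60). The window before Visit 6 is at most 180 − 60 = 120 days.

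**Size of the contrast at 30 kg.** Assume entry at 28 or 29 kg, a current level of 14.0 mg/kg/day, and a weight of 30 kg reached before Visit 6.
- 7.2: 14.0 × 28 = 392 mg/day; 14.0 × 29 = 406 mg/day.
- 6.1/6.2 with the matching level: 10.0 × 30 = 300 mg/day.
- Difference: 92 to 106 mg/day. Ratio: 392/300 = 1.31 to 406/300 = 1.35.

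The ratio is 1.4 × entry weight / 30, so it is the same at the three lower levels, which can be reached earlier.

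**The case against.** **The weights serve different purposes.** The Schedule row and most of 7.2 concern height and weight as a growth endpoint, so they need not limit weight entry in the IVRS. This is fair for the Schedule row. It fails for the last sentence of 7.2, which is about calculating the dose.

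**The IVRS is central.** One system holds the weights and assigns containers, which should reduce differences between sites. That stands as mitigation, but the documents do not show which rule it applies.

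**The 1.4-fold change at 30 kg is intended.** Correct. It reflects higher clearance per kg in smaller children, and the conflict affects only its date. A dose of 392 to 406 mg/day at 30 kg is 13.1 to 13.5 mg/kg/day. That is under the 14.0 allowed just below 30 kg and under the 15 mg/kg/day studied in A0081074, so no specific harm is shown.

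**A stronger reading.** A reader might infer a second conflict, because 14.0 − 10.0 = 4.0 mg/kg/day exceeds both increment limits (2.5 and 3.5). The documents do not support this. The Summary, 1.3 and 5.1 introduce the increments as part of flexible dosing for response and tolerability. The two sets of levels are scaled to give similar exposure, so 14.0 and 10.0 are the same rung. The taper takes 14.0 to 7.0 in one step, so the limits do not govern every dose change. What stands is that no sentence says so. The upward-only wording in 3.1 is likewise a drafting slip: the sentence before it leaves adjustment to the investigator's discretion.

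**Conclusion.** The conflict over the dosing weight is real. Following 7.2 as written leaves growing children on a dose based on a weight up to about six months old, with the drift shown above, and it delays the change at 30 kg relative to 6.1/6.2. The drift figures rest on assumed weight gains. The 30 kg contrast rests on assumed entry weights, on a child at the top level, and on the matching-level move, which is the natural reading but is not written down.

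The point is modest. The number of children affected cannot be worked out from the documents. SAP section 8 combines all pregabalin doses and plans no summary by dose, so no planned summary changes. A reader might infer that the safety results are compromised; nothing in the documents shows that. The effect is on the dose an individual child receives, and it is cheap to remove.

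**What to change.** In 7.2, replace the last two sentences with:

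> Weight is measured at every clinic visit from Visit 1 to Visit 8. The treatment-phase dose dispensed at Visits 1 to 7 is calculated from the weight at that visit. When a child first weighs 30 kg or more at one of Visits 2 to 7, the dose moves to the matching level (3.5 to 2.5, 7.0 to 5.0, 10.5 to 7.5, 14.0 to 10.0 mg/kg/day). The increment limits apply to titration for response or tolerability and not to this move.

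The move stops at Visit 7 because only taper medication is dispensed at Visit 8.

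Also:
- add weight to Visits 2, 3, 4, 5 and 7 in the Schedule of Activities and the visit lists;
- confirm that the IVRS uses the same rule;
- in 3.1, allow adjustment up or down for children of 30 kg or more, to match the Summary, 1.3 and 5.1.

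The cost is a wording amendment and an IVRS check, with reprogramming if the check finds a different rule. Weighing at every visit is already required by the notes in 6.1 and 6.2, and the SAP does not change.

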### 7.3. Clinical Laboratory Assessments

Samples for clinical laboratory measurements will be analyzed by a central laboratory.

#### Estimated Creatinine Clearance (ml/min)

Estimated Creatinine Clearance will be calculated at Screening (Visit 1A or 1B) only. For subjects who previously participated in A0081041, A0081042 or A0081105, it is assumed the subjects have already met entry criteria, therefore, the Creatinine Clearance exclusion is based upon the Screening visit of A0081041, A0081042 or A0081105. For those subjects directly enrolling into A0081106, this assessment is to be performed at Screening Visit 1B only. The estimation will be calculated by the central laboratory using the following equation, the subject's age in years and the serum creatinine value (mg/dL).

#### Converting Serum Creatinine Concentration from $\mu$ moles/L to mg/dL

$$\text{Serum Creatinine (mg/dL)} = \frac{\text{Serum Creatinine (\mu M/L)}}{88.4}$$

#### For subjects $\geq 12$ years of age

$$\text{Male CL}_{\text{CR}} = \frac{(140 - \text{age}) \times \text{Body Weight (kg)}}{72 \times \text{Serum Creatinine (mg/dL)}} \times 1.73\text{m}^2/\text{BSA}$$

$$\text{Female CL}_{\text{CR}} = \left[ \frac{(140 - \text{age}) \times \text{Body Weight (kg)}}{72 \times \text{Serum Creatinine (mg/dL)}} \right] \times 0.85 \times 1.73\text{m}^2/\text{BSA}$$
$$\text{BSA (Body Surface Area)} = 0.007184 \times \text{Height(cm)}^{0.725} \times \text{Weight(kg)}^{0.425}$$

#### For Subjects $\geq 1$ year of age and $< 12$ years of age

$$\text{Cl}_{\text{CR}} = 0.55 \times \text{length (cm)}/\text{serum creatinine (mg/dL)}$$

#### For Subjects 1 month of age and $< 1$ year of age

$$\text{Cl}_{\text{CR}} = 0.45 \times \text{length (cm)}/\text{serum creatinine (mg/dL)}, \text{ for infants 1 to } < 12 \text{ months old}$$

#### 7.3.1. Pregnancy Test

A urine pregnancy test for female subjects who are menarchal will be collected at Screening (Visit 1A and B). If the results of the urine pregnancy test are positive, the subject will not be eligible for study participation, or will need to withdraw from the study. A urine pregnancy test will also be performed at Visits 6, 7, 8, and 9. In the case of a positive urine pregnancy test, the subject can have a second confirmatory urine pregnancy test conducted locally prior to exclusion from the study. Pregnancy tests may also be performed more

frequently as per Institutional Review Board (IRB's)/Independent Ethics Committee (IEC's) or as required based upon local regulations.

### **7.3.2. Hematology**

Blood samples will be collected at Screening Visit 1A and 1B (for direct enrolling subjects only), 6 and 8 to assess hematology parameters, including: red blood cell count (RBC), hemoglobin (HGB), hematocrit (HCT), platelets, and white blood cell count (WBC) (with differential), neutrophils, lymphocytes, monocytes, basophils, and eosinophils.

Blood volumes to be obtained, per visit, are as follows:

Screening:	10.5 mL
V6:	4.5 mL
V8/ET:	10.5 mL
Unscheduled visit:	12.3 mL maximum (all testing optional)

